⁴Only applicable for women of childbearing potential. Urine pregnancy tests will be performed at all visits prior to administration of study drug. In case of a positive urine pregnancy test, a serum pregnancy test will be done. More frequent testing should be done if required by the local regulation or per investigator judgment.

C-SSRS 'since last visit' version used at all visits.

Whole blood Peripheral Blood Mononuclear Cell (PBMC) sampling should be taken approximately within 1 hour prior to administration of study drug.

¹⁰ Patients who discontinue trial treatment prematurely-should undergo the EOT visit as soon as possible and the End of Observation (EOO) Visit 4 weeks thereafter.

¹¹ Patients switching to licensed BI 730357 upon completion of active treatment in this study should not complete a washout period. Instead, their last trial visit will be EOT and trial completion will occur at that visit. These patients will not return for EOO Visit.

¹² Timing of the EOT visit is variable depending on when BI 730357 is approved and available on the market in the patient's country. Study visits (performing Visit 24 assessments and procedures) may continue every 12 weeks until licensed BI 730357 becomes available or the trial is terminated.

¹³ For patients who discontinue trial treatment prematurely, vital status will be collected once a year by telephone call starting from the last trial visit performed until the end of the originally planned observation period.

TABLE OF CONTENTS

TITLE PA	GE	1
CLINICA	L TRIAL PROTOCOL SYNOPSIS	2
FLOW CH	IART	5
TABLE O	F CONTENTS	10
ABBREVI	ATIONS	13
1.	INTRODUCTION	15
1.1	MEDICAL BACKGROUND	15
1.2	DRUG PROFILE	
1.3	RATIONALE FOR PERFORMING THE TRIAL	
1.4	BENEFIT - RISK ASSESSMENT	
2.	TRIAL OBJECTIVES AND ENDPOINTS	25
2.1	MAIN OBJECTIVES, PRIMARY AND SECONDARY ENDPOINTS	25
2.1.1	Main objectives	
2.1.2	Primary endpoint	
2.1.3	Secondary endpoints	25
3.	DESCRIPTION OF DESIGN AND TRIAL POPULATION	
3.1	OVERALL TRIAL DESIGN AND PLAN	26
3.2	DISCUSSION OF TRIAL DESIGN, INCLUDING THE CHOICE OF	• •
2.2	CONTROL GROUP(S) SELECTION OF TRIAL POPULATION	28
3.3 3.3.1		
3.3.2	Main diagnosis for trial entry Inclusion criteria	
3.3.3	Exclusion criteria	
3.3.4	Withdrawal of patients from treatment or assessments	
3.3.4.1	Discontinuation of trial treatment	
3.3.4.2	Withdrawal of consent to trial participation	
3.3.4.3	Williawai of conscit to that participation	
4	Discontinuation of the trial by the sponsor	
4.		32

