6.6.1 Efficacy data

An observed case analysis will be performed for the primary analysis of the secondary outcomes PASI 50, PASI 75, PASI 90, PASI100, and sPGA clear or almost clear endpoints at week 24.

For the secondary outcome time to loss of PASI50/PASI75/PASI90/PASI100 for patients who achieve the response up to Week 288, patients who do not have the PASI assessment performed at a visit and maintained the PASI response at all scheduled visits prior to the missing visit will be treated as censored at the day after the last visit where the PASI response was attained.

For the secondary outcome time to loss of sPGA clear or almost clear for patients who achieve the response up to Week 288, patients who do not have the sPGA assessment performed at a visit and maintained the sPGA response at all scheduled visits prior to the missing visit will be treated as censored at the day after the last visit where the sPGA response was attained.

For the secondary outcome time to loss of sPGA clear for patients who achieve the response up to Week 288, patients who do not have the sPGA assessment performed at a visit and maintained the sPGA response at all scheduled visits prior to the missing visit will be treated as censored at the day after the last visit where the sPGA response was attained.

[REDACTED]

[REDACTED]

[REDACTED]

If at any time a patient uses an inappropriate concomitant medication, then all future data will be excluded for binary variables and for continuous variables and will not be implemented beyond the date of the prohibited medication..

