6.7 BASELINE, TIME WINDOWS AND CALCULATED VISITS

For all analyses, baseline refers to the baseline value in the 1407-0030 study.

For laboratory safety measurements, the last measurements taken prior to the intake of BI 730357 or placebo will be considered as baseline.

In general, measurements reported with a date only (and no time) and taken on the day of first administration of trial treatment will also be considered pre-treatment values.

The visit schedule with accompanying details can be found in Flow Chart in the CTP. Measurements taken after start of treatment will be considered either on- or off-treatment values based on definition in [Table 6.1: 1](#).

On-treatment measurements for EOT and EOS visit for early discontinued patients will be allocated to visits by means of time windows with the limit between adjacent windows half-way between the planned dates for the visits; the middle day is counted to the window of the later visit. Mutually exclusive relative day windows are defined below to provide derived visits that correspond to the post-baseline time points. For example, Visit 2 is planned on Day 84 and Visit 3 is planned on Day 168. Therefore, the window of Visit 2 reaches until Day 125 while the window of Visit 3 starts on Day 126. The visit schedule with corresponding windows is given in the following table.

Table 6.7: 1 Time windows for patient visits

Window No.	Window label	Nominal visit	Nominal day	Interval
1	Day 1	Visit 1	1	N/A
2	Week 12	Visit 2	84	[2, 125]
3	Week 24	Visit 3	168	[126, 209]
4	Week 36	Visit 4	252	[210, 293]
5	Week 48	Visit 5	336	[294, 377]
6	Week 60	Visit 6	420	[378, 461]
7	Week 72	Visit 7	504	[462, 545]
8	Week 84	Visit 8	588	[546, 629]
9	Week 96	Visit 9	672	[630, 713]
10	Week 108	Visit 10	756	[714, 797]
11	Week 120	Visit 11	840	[798, 881]
12	Week 132	Visit 12	924	[882, 965]
13	Week 144	Visit 13	1008	[966, 1049]
14	Week 156	Visit 14	1092	[1050, 1133]
15	Week 168	Visit 15	1176	[1134, 1217]
16	Week 180	Visit 16	1260	[1218, 1301]
17	Week 192	Visit 17	1344	[1302, 1385]
18	Week 204	Visit 18	1428	[1386, 1469]
19	Week 216	Visit 19	1512	[1470, 1553]
20	Week 228	Visit 20	1596	[1554, 1637]
21	Week 240	Visit 21	1680	[1638, 1721]
23	Week 252	Visit 22	1764	[1722, 1805]
24	Week 264	Visit 23	1848	[1806, 1889]
25	Week 276	Visit 24	1932	[1890, 1973]
26	Week 288	EOT	2016	[1974, 2029]
27	Week 292	EOS	2044	[2030, ∞]

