If there are multiple values for an efficacy endpoint in one window (visit), use the one from scheduled visit. If value from scheduled visit is not present, the visit closest to the nominal day will be selected for assessing endpoints at a particular visit and for by-visit displays. If the visits are equidistant from the nominal day, then the earlier visit will be selected. All measured values will be stored in analysis datasets.

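### Read literally, SAP 6.7 and 6.6.1 censor as a responder a patient whose loss of response is first seen at an early EOT soon after an attended visit; SAP 7.5.2 leaves the point open

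*SAP*

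**What the plan says.** **Windows (SAP 6.7).** "On-treatment measurements for EOT and EOS visit for early discontinued patients will be allocated to visits by means of time windows". Boundaries lie half-way between planned days, and "the middle day is counted to the window of the later visit". The SAP's example: "Therefore, the window of Visit 2 reaches until Day 125 while the window of Visit 3 starts on Day 126".

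**Choice within a window (SAP 6.7).** "If there are multiple values for an efficacy endpoint in one window (visit), use the one from scheduled visit". A fallback covers the case with no scheduled value: "the visit closest to the nominal day will be selected for assessing endpoints at a particular visit and for by-visit displays". The section ends: "All measured values will be stored in analysis datasets".

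**Censoring (SAP 6.6.1).** A patient with a missing assessment who "maintained the PASI response at all scheduled visits prior to the missing visit will be treated as censored" on the day after the last visit in response. The two sPGA time-to-loss endpoints have parallel wording.

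**Event (SAP 7.5.2).** Time to loss runs from the first visit with the response to the date of first loss or, if censored, to the last visit with the response. Windows are not mentioned.

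**Early stoppers (Protocol Flow Chart footnote 10 and section 6.2.3).** A patient who stops treatment early "should undergo the EOT visit as soon as possible". PASI and sPGA are collected at EOT.

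**The concern.** An early EOT can fall on any day between two 12-weekly visits. It is also where loss of response is likely to be recorded, because Protocol 3.3.4.1 and 4.2.1 name intolerable worsening of psoriasis as a reason to stop treatment. If the EOT shares a window with an attended visit, the instruction to take the scheduled value passes over the EOT value. The next scheduled visit is then missing, and 6.6.1 censors the patient as still responding.

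Such censoring would be informative: patients would leave the risk set as responders because of a failure that had been measured. The error runs in one direction, towards longer durability. It would touch all six time-to-loss secondary endpoints (PASI50, 75, 90 and 100; sPGA clear or almost clear; sPGA clear).

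**Working it through.** **Inputs.** From the documents: nominal days and intervals (SAP Table 6.7: 1), the ±7-day visit allowance (Protocol Flow Chart), and an on-treatment period ending 7 days after the last dose (SAP Table 6.1: 1 with the 7-day residual effect period). Neither document gives a distribution of stopping times, so every timing below is an assumption.

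**1. Reproduce the windows.** Boundary = (day of visit k + day of visit k+1) / 2, with the middle day going to the later visit. Visits 2 and 3: (84 + 168) / 2 = 126, so Visit 2 closes on Day 125 and Visit 3 opens on Day 126, as the SAP states. All 24 intervals from Week 12 to Week 288 match the table.

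**2. Days after a visit that stay in its window.**
- Visit on its nominal day: 125 − 84 = 41; 209 − 168 = 41; 1973 − 1932 = 41.
- Visit 2 held 7 days late (Day 91): 125 − 91 = 34.
- Visit 2 held 7 days early (Day 77): 125 − 77 = 48.

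**3. Worked case.** A patient has PASI75 at Visit 3 on Day 168 and stops; the on-treatment EOT shows loss.
- EOT on Day 200 lies in [126, 209]. The Day 168 value is taken, Week 36 is missing, and 6.6.1 censors on Day 169.
- EOT on Day 210 lies in [210, 293]. No scheduled value competes, so the loss is selected and counts.

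**4. Share affected after Week 12, if time to loss uses windowed values.**
- Even spread between visits: 41/84 = 48.8%, or 41/83 = 49.4% counting only days strictly between visits.
- Uneven spread, taking the position of the EOT within the 83 days as a beta variable B and share = P(B ≤ 41/83):
  - late clustering: beta(2,1) gives (41/83)² = 24%; beta(3,1) gives (41/83)³ = 12%
  - early clustering: beta(1,2) gives 1 − (42/83)² = 74%; beta(1,3) gives 1 − (42/83)³ = 87%

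**5. Share over all early stops.** Before Visit 2 is attended the share is essentially zero: the first window is [2, 125] and the Flow Chart has no PASI or sPGA between Visits 1 and 2. Stops spread evenly over Days 2 to 2008 give 47%. Exponential stopping with assumed medians of 26, 52, 104 and 208 weeks gives 38%, 43%, 45% and 46%.

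**The case against.** The strongest reply is that the window rule was never meant for time to loss. SAP 7.5.2 works with actual dates, the only purpose given for value selection is endpoints at a particular visit and by-visit displays, and all measured values are kept. On that reading the Day 200 loss is simply the date of first loss and counts. This is a fair reading, and it stands as a possibility. It is not conclusive, because the purpose wording sits in the fallback sentence, whereas the preference for the scheduled value is stated for an efficacy endpoint without restriction.

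A second reply is that EOT is itself a Flow Chart visit. If an early EOT counts as scheduled, response was not held at all scheduled visits and the 6.6.1 censoring condition fails. The documents do not say whether it counts.

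A reader might infer more than the documents support:
- *That the SAP discards the EOT value.* It is stored; the open question is whether it is selected.
- *That half of all early-EOT losses disappear.* That needs evenly spread EOT dates and does not apply before Week 12.
- *That only the half of the interval decides.* Actual visit dates matter too. An EOT more than 7 days after the last dose is not on-treatment, and values after prohibited medication meet a separate exclusion in 6.6.1.
- *That the Kaplan-Meier curves shift by a known amount, most in the group with most stops for lack of effect.* This would need loss rates, dropout rates and the share of losses leading to a stop. The documents give none of these, and the share need not be the same for PASI50 as for PASI100.

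The trial is also descriptive, with no hypothesis test (Protocol 7.2), so no formal decision rests on these curves.

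**Conclusion.** The concern holds as a conflict, or at least an open point, between SAP 6.7 and 6.6.1 on one side and 7.5.2 on the other. Two programmers following the SAP faithfully could produce different time-to-loss curves. Under the literal window reading, a measured loss becomes a censored response for about six weeks after each attended visit from Visit 2 to Visit 24, and retained response is overstated. Under the actual-date reading, the window rule affects no losses.

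The direction under the window reading is firm. The size is not: about 49% of on-treatment early-EOT losses after Week 12 is an illustration under even timing, within about 12% to 87% under the other timings tried. I put no figure on the shift in the curves. The point goes beyond missing detail, because a stated selection rule can lead to a result biased towards durability.

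**What to change.** - **SAP 6.7 and 7.5.2, add:** *Window selection applies only to by-visit summaries and to endpoints at a given visit. Time-to-loss endpoints use every dated on-treatment PASI or sPGA assessment, including early EOT and unscheduled visits; the first assessment without the response is the event.*
- **SAP 6.6.1:** in the three time-to-loss paragraphs, replace the reference to all scheduled visits with all available assessments. This also removes the need to decide whether an early EOT is a scheduled visit.

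The cost is a few sentences in the SAP and matching program specifications. The values are already collected and stored. An EOT more than 7 days after the last dose would still not be used, because the on-treatment limit stays.

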7. PLANNED ANALYSIS

The format of the listings and tables will follow the standards defined in the BI corporate guideline “Reporting of clinical trials and project summaries” .

The individual values of all patients will be listed, sorted by treatment, patient number and visit. The listings will be included in Appendix 16.2 of the CTR.

For EoT tables, the set of summary statistics is: N / Mean / SD / Min / Median / Max.

For appendix tables, the set of summary statistics is: N / Mean / SD / Min / Q1 (lower quartile) / Median / Q3 (upper quartile) / Max.

Tabulations of frequencies for categorical data will include all possible categories and will display the number of observations in a category as well as the percentage (%) relative to the respective treatment group. Percentages will be rounded to one decimal place. The category “missing” will be displayed only if there are actually missing values. Percentages will be based on all patients in the respective patient set no matter whether they have non-missing values or not.

No interim analysis is planned for this trial.

For patients from Part 1 of the 1407-0030 trial planned treatment for first 12 weeks of treatment is defined as treatment patient received at the end of 1407-0030. Planned treatment for after 12 weeks (Period 2) is defined as the treatment patient assigned from IVRS at week 12 visit (V2). For patients who titrate according to the protocol from 100 g *q.d.* dose to 200 g *q.d.* dose, if the investigator determines that the patient may benefit from the higher dose, 200 g *q.d.* dose will be the planned dose after the titration.

Subject data listings of data used in the analyses (i.e. demographic and baseline characteristics and key efficacy endpoints) will also be provided and included in Appendix 16.2 of the CTR.

Disposition of the patient population participating in the trial will be summarised by presentation of the frequency of patients screened, entered, screened but not entered, treated, entered but not treated. Within treated patients, data for patients rolled over from Part 1 of trial 1407-00030 will be summarized by treatment periods (period 1 - first 12 weeks of treatment and period 2 – open label treatment after week 12) for treatment ongoing patients, patients complete planned treatment period and patients who are prematurely discontinued, by reason.

Because there is no scheduled titration for patients from Part 2 of trial 1407-0030 disposition will be summarized without distinguishing the first 12 weeks from after 12 weeks for these patients.

7.1 DEMOGRAPHIC AND OTHER BASELINE CHARACTERISTICS

Only descriptive statistics are planned for this section of the report. Demographic parameters collected and to be presented include, but are not limited to, the following:

- Gender (Male, Female)
- Race and ethnicity (as defined in the eCRF)
- Age [years]
- Height [cm]
- Weight [kg]
- Body mass index [kg/m²] (defined as weight [kg]/(height [cm]/100)²)
- Smoking history (Never-smoked, Ex-smoker, Currently smokes)
- Alcohol History (Non-drinker, drinks – no interference, drinks – possible interference)
- Region
- PsA history (diagnosed, suspected, no PsA)
- Prior biologic use for psoriasis (Yes/No)

Baseline disease characteristic to be presented include, but are not limited to, the following:

- PASI score
- Body surface area (affected by plaque psoriasis)
- sPGA

Number (%) of patients with psoriasis therapy history will be summarized, including both non-topical drug therapy and non-drug therapy.

7.2 CONCOMITANT DISEASES AND MEDICATION

Only descriptive statistics are planned for this section of the report.

A table of the number (%) of patients with concomitant diagnoses from baseline condition by system organ class (SOC) and preferred term (PT) will be included along with a supporting listing. Concomitant diagnoses will be coded with the most recent version of MedDRA in effect at database lock.

Concomitant medication will be described as a table of number (%) of patients with on-treatment medication use. On-treatment is defined as medication with a stop date after or on the day of first trial drug intake and before last trial drug intake + 7 days.

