1.2 DRUG PROFILE

Residual Effect Period

The Residual Effect Period (REP) of BI 730357 is 7 days. This is the period after the last dose with measurable drug levels and/or pharmacodynamic effects still likely to be present.

06 Oct 2020

Page 17 of 84

Clinical Trial Protocol

Page 18 of 84

Clinical Trial Protocol

Page 19 of 84

Page 20 of 84

Page 21 of 84

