4.2 OTHER TREATMENTS, EMERGENCY PROCEDURES, RESTRICTIONS

4.2.1 Other treatments and emergency procedures

Stable doses of concomitant therapies for chronic conditions, for which neither the condition nor the treatment are judged to exclude the patient from participation (cf. Section 3.3) may be permissible. All concomitant medications should be carefully evaluated by the Investigator and the Clinical Monitor Local (CML) should be contacted when there are questions regarding concomitant medications.

In the event that a patient experiences an intolerable increase of PsO during the course of the trial, the trial medication will be discontinued and anti-psoriatic agents may be used as rescue medications. Refer to Section 6.2.3 for early treatment and trial termination instructions.

In case of any AEs in need of treatment, symptomatic therapy according to investigator judgment will be permitted. All concomitant and/or rescue therapies will be recorded on the appropriate pages of the electronic case report form (eCRF).

Severe infections according to RCTC grading, serious infections, and opportunistic or mycobacterial infections:

Treatment of the infection should be initiated promptly according to local standard of care. Treatment with trial medication should be discontinued.

Clinical Trial Protocol Page 38 of 84

Malignancies

c22181693-04

In case of occurrence of malignant neoplasm other than appropriately treated basal cell carcinoma or squamous cell carcinoma of the skin or in situ carcinoma of uterine cervix, the investigator should discontinue treatment with the trial medication, and notify the CML. Diagnostics and treatment should be initiated according to local standard of care.

Suicidality

In case of signals of suicidal ideation the patient should be referred to a mental health professional for further work-up.

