- Serious adverse events (onset date (mandatory), and end date (if available))
- Concomitant therapy (start date, changes)
- Originals or copies of laboratory results and other imaging or testing results, with proper documented medical evaluation (in validated electronic format, if available)
- Completion of patient's participation in the trial" (end date; in case of premature discontinuation document the reason for it).
- Prior to allocation of a patient to a treatment into a clinical trial, there must be documented evidence in the source data (e.g. medical records) that the trial participant meets all inclusion criteria and does not meet any exclusion criteria. The absence of records (either medical records, verbal documented feedback of the patient or testing conducted specific for a protocol) to support inclusion/exclusion criteria does not make the patient eligible for the clinical trial.

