It is expected that Visit 1 of trial 1407-0005 will be performed on the same day of the EOT Visit of trial 1407-0030 in both patient groups. In the event that patients completing Part 2 of trial 1407-0030 are not able to be entered immediately into the extension trial due to administrative reasons (e.g., pending protocol approval, availability of trial medication), Visit 1 of the extension trial may be delayed for no more than 16 weeks.

The treatment period in this trial will be approximately 6 years.

Figure 6.1: 1

Trial 1407-0005 dose assignment/reassignment for patients entering from Part 1 of trial 1407-0030

[figure not shown]
[figure not shown]

Figure 6.1: 2

Trial 1407-0005 dose assignment for patients entering from Part 2 and continuing from Part 1 of trial 1407-0030

Dose selection at Week 12 is based on the safety and tolerability data from the SRD Trial 1407.1 and the MRD Trial 1407-0002, and will be contingent on DMC evaluation of all available data from Phase II trial 1407-0030. For patients entering from Part 1 of trial 1407-0030, if an unacceptable risk regarding the safety of the 200 mg dose level is reported by the DMC, the open label BI 730357 dose assignments beginning at Week 12, is to be altered to assign all patients to the 100 mg *q.d.* dose group.

All patients entering from Part 2 of trial 1407-0030 are to receive the 400 mg *q.d.* dose, as long as no unacceptable risks are identified during Part 2 of trial 1407-0030. Once Part 2 patients begin enrolling in this trial, existing patients receiving 100 mg *q.d.* in this trial will be given the option to titrate up to the 200 g *q.d.* dose, if the investigator determines that the Patients may benefit from the higher dose.

The first Part 2 patients enrolled in this study on December 10, 2020 and at that time all Part 1 patients had been in the study more than 12 weeks and had titrated to 100 mg *q.d.*

Subjects will be analyzed according to the treatment to which they were treated. The following study periods based on actual start and stop dates of study treatment administration are defined as follow.

Table 6.1: 1 Definition of Treatment Periods

Analysing Treatment Period	Start Date	Stop Date
Screening [#]	NA	NA
On-treatment*	Date/Time of the first administration of trial treatment	Date of the last administration of trial treatment + REP
Follow-up	Date of the last administration of trial treatment + REP+1 day	Date of the last per protocol visit

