6.6.2 Safety data and other data

In general, missing data will not be imputed and only observed values will be analyzed.

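### SAP 7.2 defines on-treatment concomitant medication by stop date alone, so ongoing drugs and drugs stopped 7 or more days after last intake fall out of the summary table

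*SAP*

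**What the plan says.** SAP 7.2 (Concomitant diseases and medication) describes one output for co-medication: "Concomitant medication will be described as a table of number (%) of patients with on-treatment medication use". It then defines on-treatment as "medication with a stop date after or on the day of first trial drug intake and before last trial drug intake + 7 days".

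The surrounding text matters in four ways.

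- **On-treatment period.** SAP Table 6.1: 1 ends the on-treatment period at "Date of the last administration of trial treatment + REP" and starts follow-up one day later. Protocol 1.2 gives the length: "The Residual Effect Period (REP) of BI 730357 is 7 days".
- **What is allowed and recorded.** Protocol 4.2.1 says that "Stable doses of concomitant therapies for chronic conditions" may be permissible, and that "All concomitant and/or rescue therapies will be recorded on the appropriate pages of the electronic case report form". The Flow Chart collects concomitant therapy at every visit, up to and including EOO at Week 292.
- **Which dates are named.** The source-data list in Protocol 8.3.1 has an entry that reads "Concomitant therapy (start date, changes". It does not name a stop date.
- **Missing data.** SAP 6.6.2 states: "In general, missing data will not be imputed and only observed values will be analyzed". The only date-imputation rule in the visible text, SAP 6.6.3, is for adverse event dates.

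**The concern.** A drug is concomitant with treatment if the interval in which it was taken overlaps the treatment period. That test needs two comparisons on two different dates: the drug started before the period ended, and it had not stopped before the period began. SAP 7.2 makes both comparisons on the stop date, so it selects drugs that ended during the period instead of drugs that were used during it.

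In a trial planned to run for about 6 years, the two are not the same. A table built this way favours completed courses over continuing therapy. It could give a reader of the long-term safety data a distorted picture of background medication.

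**Working it through.** The plan states no figure to reproduce, so the check is one of logic.

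**Inputs.** F = day of first intake and L = day of last intake. For illustration F = 1 and L = 2016, the nominal EOT day in SAP Table 6.7: 1. The 7 days come from SAP 7.2 and Protocol 1.2, so L + 7 = 2023. Week 292 is Day 2044 in the same table, which is L + 28.

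**Rules compared.**

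- SAP 7.2 as written: F ≤ stop < L + 7, that is, 1 ≤ stop < 2023.
- Overlap: start ≤ L + 7, and either stop ≥ F or ongoing.

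**Constructed records.**

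| Record | Start | Stop | SAP 7.2 as written | Overlap |
|---|---|---|---|---|
| Chronic drug, ongoing | −300 | none | out | in |
| Same drug, stop date set to the Week 292 day | −300 | 2044 | out | in |
| Started on treatment, ongoing | 500 | none | out | in |
| Started before, stopped mid-treatment | −300 | 500 | in | in |
| Short course | 500 | 510 | in | in |
| Stopped at L + 6 | 500 | 2022 | in | in |
| Stopped at L + 7 | 500 | 2023 | out | in |
| Stopped at L + 8 | 500 | 2024 | out | in |
| Stopped at L + 20 | 500 | 2036 | out | in |
| Stopped before first intake | −300 | 0 | out | out |
| Started after L + 7 | 2026 | none | out | out |

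Three things follow.

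1. An ongoing drug fails either way. Without a stop date there is nothing to compare, and a stop date set to the end of observation breaches the upper limit (2044 is not below 2023).
2. The loss begins at exactly 7 days after last intake, because the rule says before and not on or before. Table 6.1: 1 counts that day as on-treatment, so the two sections differ by one day as well as in the date they test.
3. The error runs one way. Any record the written rule accepts has start ≤ stop < L + 7 and stop ≥ F, so the overlap rule accepts it too. The written rule can omit on-treatment medication, but it cannot add any.

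Stop dates after L + 7 can arise in practice. Protocol 6.2.3 places EOO 4 weeks after the last dose for patients who stop early, and concomitant therapy is still collected at that visit.

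**The case against.** The strongest answer is that this is a drafting slip. The sentence reads like an overlap rule from which a reference to the start date has been lost. An experienced programmer might apply the overlap rule anyway, and SAP 7 says that tables follow a corporate reporting guideline, which is not available here. That is plausible, and Table 6.1: 1 suggests the same intent. But the SAP states its own explicit rule, and nothing in the visible text replaces it. The consequence depends on the rule being applied literally, and that condition belongs with the finding.

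Three stronger readings are tempting, and the documents do not support them.

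- **That the efficacy or primary results are affected.** They are not. SAP 7.4.1 (TEAE rate) and 7.5.2 (Week 24 response and time to loss of response) do not use this definition. SAP 6.6.1 handles efficacy data after an inappropriate concomitant medication by a separate rule that does not refer to 7.2.
- **That anti-psoriatic therapy bearing on loss of response would be hidden.** Protocol 4.2.1 and 4.2.2.1 tie rescue use to discontinuation of trial medication. Rescue begun within 7 days of the last dose and then continued would drop out of the table, but that is a narrow case, and the records remain in the eCRF.
- **That nearly all chronic medication, or some number of patients, would be lost.** The documents give no proportion of patients on chronic drugs, and the 270 patients are a ceiling. A patient with a chronic drug and one short course would still appear, though not under the chronic drug. If a dose change closes a CRF record, which cannot be seen from here, part of a chronic drug's history would have a qualifying stop date.

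**Conclusion.** Wrong as written, of minor severity. Followed literally, SAP 7.2 excludes from its only concomitant-medication table any record with no stop date because the drug is ongoing, and any on-treatment drug stopped 7 or more days after last intake. The direction is certain (omission only). The size cannot be computed, because the documents contain no medication counts.

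The effect stops at this descriptive table. SAP 7 provides for individual values of all patients to be listed, so the summary would be incomplete but the data would not be lost. The conclusion rests on two assumptions: that the table is programmed from the sentence as it stands, and that no unseen standard overrides it.

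**What to change.** Replace the definition in SAP 7.2 with an overlap rule. A medication is on-treatment if its start date is on or before last trial drug intake + 7 days, and either its stop date is on or after first trial drug intake or it is recorded as ongoing. Making the upper limit inclusive also aligns it with Table 6.1: 1.

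State the convention for missing or partial start and stop dates separately, because SAP 6.6.2 in general rules out imputation and 6.6.3 covers adverse event dates only. One option is to count the medication as on-treatment unless the available date parts show otherwise.

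The cost is about two sentences in the SAP and a small change to one derivation. The one choice to make is the missing-date convention, since counting such records as on-treatment may include a few drugs that were not.
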